7.5.1.7 Rate of Decrease in BKV Plasma Viral Load by Visit

Rate of decrease in BKV plasma viral load is calculated using the following formula:

Rate of decrease = Change from baseline (copies/mL) / time (weeks) between baseline and post-baseline.

The BKV plasma viral load at 1 week, 2 weeks, 4 weeks, 8 weeks, 12 weeks, 16 weeks and 36 weeks with LOCF, change from baseline and rate of decrease will be summarized with descriptive statistics.

Treatment difference in the rate of decrease between each treatment dose group and combined placebo group will be assessed at the specified visit with LOCF using an ANOVA model with treatment (four levels) as a factor. The least squares (LS) mean, SE, 95% CI, and p-value will be obtained from the model estimates. The normality of the residuals from the ANOVA model will be assessed using the Shapiro-Wilk statistic and graphical examination. If data shows significant deviation from normality, the Wilcoxon rank sum test will be applied if necessary.

In addition, the pairwise treatment differences will be analysed using the two-sample t test. The p-value from each t test will be presented.

7.5.1.8 Change in eGFR from Baseline to Week 12, Week 16 and Week 36

eGFR is calculated using the CK-EPI equation. The eGFR at Week 12, Week 16 and Week 36 with LOCF, change from baseline will be summarized with descriptive statistics.

Treatment difference in the eGFR change from baseline between each treatment dose group and combined placebo group will be assessed at Week 12, Week 16 and Week 36 with LOCF using an ANOVA model with treatment (four levels) as a factor. The LS mean, SE, 95% CI, and p-value will be obtained from the model estimates. The normality of the residuals from the ANOVA model will be assessed using the Shapiro-Wilk statistic and graphical examination. If data shows significant deviation from normality, the Wilcoxon rank sum test will be applied if necessary.

In addition, the pairwise treatment differences will be analysed using the two-sample t test. The p-value from t test will be presented.

7.5.1.9 Proportion of Subjects with BKV Nephropathy by Week 12, Week 16 and Week 36

The number and percentage of subjects with BKV nephropathy by Week 12, Week 16 and Week 36 based on renal biopsy, clinical diagnosis or other method of diagnosis as reported in the eCRF

will be tabulated and summarized by whether BKV nephropathy was confirmed by biopsy or diagnosed clinically in the absence of biopsy results. All instances of biopsies demonstrating BKV nephropathy will be reported in the CSR, however cases of biopsy-proven BKV nephropathy in patients with no pre-study biopsy, stable or improvement serum creatinine and improving BKV plasma viral loads will be excluded from the summary to avoid counting patients who most likely had BKV nephropathy prior to study entry. Exclusion of these patients from the summary will be based on the opinion of the SSRC and documented.

The method of diagnosis during the study reported in eCRF will be summarized at an overall post-baseline visit. If the subjects have different methods of diagnosis reported at different post-baseline visits, the same subject will be counted in the different methods of diagnosis.

The proportion of subjects with BKV nephropathy by Week 12, Week 16 and Week 36 will be analyzed using a logistic regression model with treatment (four levels) as a factor. For the treatment comparison between each treatment dose group and combined placebo group, the estimated odds ratio, 95% CI, and p-value will be presented.

In addition, the pairwise treatment comparisons in the proportion will be made using Fisher's Exact Test. The treatment difference estimates, the exact 95% CI, and p-values from Fisher's Exact Test will be presented.

7.5.1.10 Proportion of Subjects with Graft Failure by Week 12, Week 16 and Week 36

The number and percentage of subjects with graft failure (i.e., permanent requirement for renal replacement therapy) by Week 12, Week 16 and Week 36 will be tabulated.

The proportion of subjects with graft failure by Week 12, Week 16 and Week 36 will be analyzed using a logistic regression model with treatment (four levels) as a factor. For the treatment comparison between each treatment dose group and combined placebo group, the estimated odds ratio, 95% CI, and p-value will be presented.

In addition, the pairwise treatment comparisons in the proportion will be made using Fisher's Exact Test. The treatment difference estimates, the exact 95% CI, and p-values from Fisher's Exact Test will be presented.

7.5.1.11 Proportion of Subjects with Acute Rejection by Week 12, Week 16 and Week 36

The number and percentage of subjects with acute rejection (based on kidney biopsy results and 2017 Banff Kidney Meeting Report) by Week 12, Week 16 and Week 36 will be tabulated.

The proportion of subjects with acute rejection by Week 12, Week 16 and Week 36 will be analyzed using a logistic regression model with treatment (four levels) as a factor. For the treatment comparison between each treatment dose group and combined placebo group, the estimated odds ratio, 95% CI, and p-value will be presented.

In addition, the pairwise treatment comparisons in the proportion will be made using Fisher's Exact Test. The treatment difference estimates, the exact 95% CI, and p-values from Fisher's Exact Test will be presented.

7.5.1.12 Mortality Rate/Survival by Week 12, Week 16 and Week 36

Time (weeks) to death is defined as the number of days from first dose date of study drug to the date of death during the study plus 1, then divided by 7.

Subjects who are alive by Week 12, Week 16 and Week 36, not known to die, or lost to follow-up will be censored on the last date the subject is known to be alive.

The number and percentage of subjects who died by Week 12, Week 16 and Week 36 and subjects who are censored will be tabulated. Time (weeks) to death will be summarized using descriptive statistics.

The median time to death by Week 12, Week 16 and Week 36 and associated 95% CI will be estimated for each treatment group using the Kaplan-Meier method. The estimate of the hazard ratio for the treatment comparison between each treatment dose group and the combined placebo group along with the 95% CI will be calculated using a Cox proportional hazard model with treatment (four levels) as a factor. The log-rank p-value for the treatment comparison will be presented as well.

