7.1.5 Handling of Dropouts and Missing Data

For Viracor/Eurofins BK viral load test results in both plasma and urine, the non-numerical results will be imputed as below in the analysis:

- ‘Detected:<39 copies/mL’ will be imputed as ‘38 copies/mL’ for plasma;
- ‘Detected:<61 copies/mL’ will be imputed as ‘60 copies/mL’ for urine;
- ‘Not Detected’ will be imputed as ‘25 copies/ mL’; and
- ‘>1.00E+10 copies/ mL’ will be imputed as ‘10¹⁰+1 copies/ mL’.

If there are multiple BK viral load test results for a single timepoint from both initial and back-up samples, the result from the back-up sample will be used in the analysis. If there are exceptions that require a different rule, it will be documented separately for the scenarios.

For Viracor/Eurofins BK viral load test results in both plasma and urine, missing data at each scheduled post-baseline visit will be imputed using the last post-baseline observation carried forward (LOCF) in the analysis.

Subjects who dropped out or had missing data will be included in the denominator for safety and efficacy analyses as described in Section 7.2.

In cases of missing or incomplete dates (e.g. Adverse event [AE] and concomitant medications), the missing component(s) will be assumed as the most conservative value possible. For example, AEs with missing start dates, but with stop dates either overlapping into the treatment period or missing, will be counted as treatment-emergent, taking the worst-case approach. When partial dates are present in the data, both a partial start date and/or a partial stop date will be evaluated to determine whether it can be conclusively established that the AE started prior to the start of study drug or ended prior to the start of study drug. If the above cannot be conclusively established based on the partial and/or present dates, then the AE will be considered as treatment-emergent. Actual data values as they appear in the original eCRF will be presented in the data listings.

Missing values for other variables will not be imputed and only observed values will be used in data analyses and summaries.

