7.5.1.2 Time (weeks) to First Decrease of BKV Plasma Viral Load to <LLOQ

The lower limit of quantitation (LLOQ) of BKV plasma viral load is 39 copies/mL BK virus DNA detected <LLOQ will be reported as 'Detected:<39 copies/mL' in data.

Time (weeks) to first decrease of BKV plasma viral load to <LLOQ is defined as the number of days from first dose date of study drug to the first decrease of BKV plasma viral load to <LLOQ during the study plus 1, then divided by 7.

Subjects who did not have a decrease of BKV plasma viral load to <LLOQ at any post-baseline visits, discontinued from the study, or died will be considered censored. For the censored subjects, the last assessment date will be used as the date of censoring.

The number and percentage of subjects with a decrease of BKV plasma viral load to <LLOQ during the study and subjects who are censored will be tabulated. Time to first decrease of BKV plasma viral load to <LLOQ will be summarized using descriptive statistics.

The median time to first decrease of BKV plasma viral load to <LLOQ and associated 95% CI will be estimated for each treatment group using the Kaplan-Meier method. The estimate of the hazard ratio for the treatment comparison between each treatment dose group and the combined placebo group along with the 95% CI will be calculated using a Cox proportional hazard model with treatment (four levels) as a factor. The log-rank p-value for the treatment comparison will be presented as well.

Time (weeks) to first decrease of BKV plasma viral load to <LLOQ will also be summarized by baseline BKV genotype.

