7.5.1.3 Time (weeks) to First Decrease of BKV Plasma Viral Load to <LOD

The limit of detection (LOD) of BKV plasma viral load is 26 copies/mL. BK virus DNA detected <LOD will be reported as 'Not Detected' in data.

Time (weeks) to first decrease of BKV plasma viral load to <LOD is defined as the number of days from first dose date of study drug to the first decrease of BKV plasma viral load to <LOD during the study plus 1, then divided by 7.

Time (weeks) to first decrease of BKV plasma viral load to <LOD will be analyzed in the same manner as Time (weeks) to first decrease of BKV plasma viral load to <LLOQ.

7.5.1.4 Proportion of Subjects with ≥ 1 log Decrease of BKV Plasma Viral Load by Visit

The number and percentage of subjects with ≥ 1 log decrease of BKV plasma viral load by 1 week, 2 weeks, 4 weeks, 8 weeks, 12 weeks, 16 weeks and 36 weeks will be tabulated. The last observation by the specified timepoint will be used to identify ' ≥ 1 log decrease of BKV plasma viral load'.

The proportion of subjects with ≥ 1 log decrease of BKV plasma viral load by the specified visit will be analyzed using a logistic regression model with treatment (four levels) as a factor. For the treatment comparison between each treatment dose group and combined placebo group, the estimated odds ratio, 95% CI, and p-value will be presented.

In addition, the pairwise treatment comparisons in the proportion will be made using Fisher's Exact Test. The treatment difference estimates, the exact 95% CI, and p-values from Fisher's Exact Test will be presented.

The proportion of subjects with ≥ 1 log decrease of BKV plasma viral load by the specified visit will also be summarized by baseline BKV genotype.

7.5.1.5 Proportion of Subjects with Decrease of BKV Plasma Viral Load to <LLOQ by Visit

The number and percentage of subjects with decrease of BKV plasma viral load to <LLOQ by 1 week, 2 weeks, 4 weeks, 8 weeks, 12 weeks, 16 weeks and 36 weeks will be tabulated. The last observation by the specified timepoint will be used to identify 'decrease of BKV plasma viral load to <LLOQ'.

The proportion of subjects with decrease of BKV plasma viral load to <LLOQ by the specified visit will be analyzed using a logistic regression model with treatment (four levels) as a factor. For the treatment comparison between each treatment dose group and combined placebo group, the estimated odds ratio, 95% CI, and p-value will be presented.

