7.5.2.3 Viral Kinetics of BKV in Plasma and Urine

The BKV plasma and urine viral load, change from baseline and rate of decrease over time by 1 week, 2 weeks, 4 weeks, 8 weeks, 12 weeks, 16 weeks and 36 weeks will be summarized with descriptive statistics. Missing data at each scheduled post-baseline visit will be imputed using the LOCF approach. The corresponding line plots of the plasma and urine BKV viral load over time will be presented by treatment group and study visit.

All plasma and urine BKV viral load data will be listed by treatment and subject.

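### The rate of decrease is computed in copies/mL over all weeks since baseline, so it mainly reflects baseline load; log10 alone would leave a second, floor-related loss

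*SAP*

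**What the plan says.** SAP 7.5.1.7 gives the formula "Rate of decrease = Change from baseline (copies/mL) / time (weeks) between baseline and post-baseline". The comparison of each dose group with pooled placebo "will be assessed at the specified visit with LOCF using an ANOVA model with treatment (four levels) as a factor", at Weeks 1, 2, 4, 8, 12, 16 and 36. A Wilcoxon test is the fallback for non-normal residuals, and pairwise two-sample t tests are added.

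Three further rules shape the result:
- SAP 7.5.1.3: "The limit of detection (LOD) of BKV plasma viral load is 26 copies/mL". SAP 7.5.1.2: "The lower limit of quantitation (LLOQ) of BKV plasma viral load is 39 copies/mL". Under SAP 7.1.5 a Not Detected result is analysed as 25 copies/mL, so the recorded load cannot fall further. Nothing stops the clock in the denominator at that point.
- SAP 7.1.5: "missing data at each scheduled post-baseline visit will be imputed using the last post-baseline observation carried forward (LOCF) in the analysis". Section 7.5.1.7 does not say whether the time for a carried-forward value is the nominal visit or the actual sample time.
- SAP 7.5.2.3 summarises "change from baseline and rate of decrease over time by 1 week, 2 weeks, 4 weeks" and later visits, for plasma and urine. SAP 8.2.2 puts the plasma rate through Week 12 into the second interim analysis, analysed as in 7.5.1.

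**The concern.** The endpoint should show whether MAU868 makes the virus fall faster. Viral decline is roughly proportional, and the neighbouring endpoints treat it so by counting 1 log falls. A difference in copies/mL is governed by the starting value instead. Eligible baselines span about four logs: at least 10^3 copies/mL for the MITT population (SAP 7.2.2) and below 10^7 (protocol exclusion criterion 2).

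The likely error is a false negative. A real difference in speed could be reported as no difference in rate, both in the final analysis and at the second interim review, whose efficacy conclusions may feed into the regimen for Cohort 3 (SAP 8.2).

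**Working it through.** The documents state no expected rate, SD or power for this endpoint, so there is no figure of theirs to reproduce.

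**1. Scale.** Take baseline 10^B and decline of s log10/week, so V(t) = max(10^(B − s·t), 25). Above the floor, change = 10^B × (1 − 10^(−s·t)). A 1 log fall gives 1 − 0.1 = 90% of baseline; a 2 log fall gives 99%.

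For a subject falling twice as fast from the same baseline, the ratio of the two SAP rates is (1 − 10^(−2st)) / (1 − 10^(−st)) = 1 + 10^(−st). It should be 2. At Week 8:
- s = 0.05: 1 + 10^(−0.4) = 1.40
- s = 0.1: 1 + 10^(−0.8) = 1.16
- s = 0.2: 1 + 10^(−1.6) = 1.03

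The last case needs no floor. From 10^6 copies/mL at 0.2 and 0.4 log10/week, the floor is reached only at Weeks 23.0 and 11.5. On log10 the Week 8 ratio there is still 2.0.

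Baseline dominates between subjects. From 10^6, a half-log fall is 10^6 × (1 − 10^(−0.5)) = 683,772 copies/mL. From 10^4, complete clearance is 10,000 − 25 = 9,975. At the same visit the first subject's rate is 683,772 / 9,975, or about 69 times as large, although the second has cleared.

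**2. Floor.** Subjects A and B both start at 10^4; A is Not Detected from Week 1, B only from Week 12. At Week 12 both score 9,975/12 = 831 copies/mL per week. On log10 both score (4 − 1.40)/12 = 0.22. They also tie at Weeks 16 and 36 on either scale.

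**3. Power.** Assumptions: baseline uniform on 3.5 to 6 log10; linear log10 decline to log10(25); between-subject SD of speed about two-thirds of the slower speed (for example 0.2 at 0.3 log10/week); SD of change 0.2; no dropout; 8 vs 12 subjects; two-sided t test at 0.05. The documents give no decline speed (protocol 1.1 says only that clearance takes months), so a range is shown.

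| Speeds (log10/week) | SAP rate, copies/mL, any visit | log10 rate, Week 8 / 12 / 36 |
|---|---|---|
| 0.05 vs 0.1 | at most about 10% | 66% / 77% / 72% |
| 0.1 vs 0.2 | at most about 10% | 79% / 81% / 24% |
| 0.2 vs 0.4 | at most about 10% | 80% / 59% / 5% |
| 0.3 vs 0.6 | at most about 10% | 53% / 23% / 4% |

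A repeat simulation agreed with the log10 figures to within about four percentage points. The Wilcoxon fallback on the copies/mL rate reaches at most about 15%.

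**4. Alternative.** A least-squares slope of log10 load on time was fitted per subject on the scheduled visits (Weeks 0 to 6, 8, 10, 12), ending at the first value below 39 copies/mL. Power is about 79% to 88% across the four settings. At 0.3 vs 0.6 it recovers 0.29 vs 0.57 log10/week.

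**5. Carried-forward values.** If the denominator were the actual sample time, a subject leaving after Week 4 would get a Week 36 rate 36/4 = 9 times that of a completer with the same fall. With nominal time the factor is 1. The text permits either.

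**The case against.** Speed is already measured elsewhere. Times to a 1 log decrease, to <LLOQ and to <LOD (SAP 7.5.1.1 to 7.5.1.3) are not diluted by weeks after clearance and would separate subjects A and B. The endpoint is secondary, and SAP 3 says the study is not powered for efficacy. All of this stands and limits the priority of the point.

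A reader might infer that the denominator weakens the test. It does not: at a common visit time, dividing by weeks divides every value by the same constant, so the ANOVA, t-test and Wilcoxon p-values equal those for change from baseline. Saturation of the change costs the power. The consequence is that the late-visit rate adds nothing to change from baseline.

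A reader might also infer that the rate works early and stops measuring speed from Week 8. The documents support neither half. As written, in copies/mL, power is low at every visit, including Weeks 1 to 4. On log10, the week at which the difference fades depends on an unstated speed: at 0.1 vs 0.2 log10/week, power is still about 80% at Weeks 8 and 12.

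The ninefold carried-forward effect depends on a reading the SAP leaves open, so it is an ambiguity and not an established error.

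**Conclusion.** The point holds as a correction to a secondary endpoint. The copies/mL scale is the main defect: under the stated assumptions a two-fold difference in speed is detected about 10% of the time or less at every visit. Time at the floor is the second defect, and changing only to log10 would leave it: Week 36 power is then about 4% to 24% for slower-arm speeds of 0.1 log10/week or more, against 72% at 0.05 vs 0.1.

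The algebra in steps 1 and 2 needs only proportional decline and the SAP's own floor. The power figures rest on assumed speeds, baselines and variability. It does not follow that the trial cannot show faster clearance, because the time-to-event endpoints remain.

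**What to change.** Replace the formula in SAP 7.5.1.7 with one slope per subject: the least-squares slope of log10 plasma load on actual sample time, from baseline through the first value <LLOQ, or through Week 12 if the load never falls below LLOQ. Use no carried-forward values, and report a fall as a positive rate, since the present formula leaves the sign undefined and a post-minus-baseline change would make a fall negative. Compare slopes between groups with the planned four-level model. Keep log10 change from baseline by visit as the description, including Weeks 16 and 36. Apply the same definition in 7.5.2.3 (with the urine LLOQ for urine) and in the second interim analysis (8.2.2), and list the change in SAP 9.

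The cost is SAP wording and one derivation from samples already scheduled; the SAP is finalised only before database lock (SAP 1). Two small drawbacks: a subject who clears by Week 1 has a two-point slope, and the slope is slightly underestimated when decline is fast (0.57 against a true 0.60 log10/week above).

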3 SAMPLE SIZE DETERMINATION

This study will randomize approximately 36 subjects (12 per cohort) to MAU868 and placebo in a 2:1 ratio (24 MAU868 and 12 placebo; 8 MAU868 and 4 placebo per cohort). This study is not powered to an efficacy endpoint. The number of subjects chosen will provide data useful in determining proof of concept.

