7.5 Efficacy Assessment

The efficacy analysis will be performed based on the MITT Population and will be repeated on the ITT Population.

In efficacy analyses, pairwise contrasts comparing each of the three active groups to the combined placebo group will be tested. Efficacy analyses will be conducted using two sided tests at the alpha=0.05 level of significance, with no adjustment for multiplicity.

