8.2.2 Cohorts 1 & 2: Response to Study Treatment

The following efficacy endpoints are included in the second interim analysis and will be assessed by the SSRC for subjects in Cohorts 1 and 2. The analysis will be performed based on the MITT Population and will be repeated on the ITT Population.

- Time (weeks) to decrease of BKV plasma viral load by 1 log;
- Time (weeks) to first decrease of BKV plasma viral load to <LLOQ ;
- Proportion of subjects with ≥ 1 log decrease of BKV plasma viral load by 1 week, 2 weeks, 4 weeks, 8 weeks, and 12 weeks;
- Proportion of subjects with decrease of BKV plasma viral load to <LLOQ by 1 week, 2 weeks, 4 weeks, 8 weeks, and 12 weeks;
- Rate of decrease in BKV plasma viral load by 1 week, 2 weeks, 4 weeks, 8 weeks, and 12 weeks;
- Change in eGFR from baseline to week 12;
- Proportion of subjects with BKV nephropathy through week 12;
- Proportion of subjects with graft failure through week 12;
- Proportion of subjects with acute rejection through week 12;
- Proportion of subjects who have died through week 12.

In the efficacy analyses, pairwise contrasts comparing each of the two active groups to the combined placebo group will be tested. The treatment groups will be 3 levels (i.e. Cohort 1 active group, Cohort 2 active group and combined placebo group). The analyses will be conducted using two sided tests at the alpha=0.05 level of significance, with no adjustment for multiplicity.

The efficacy endpoints above for the second interim analysis will be summarized and analyzed in the same manner as described in Section 7.5.1 with the exception that Cohort 3 subjects will not be included in the interim analysis.

8.2.3 Pharmacokinetics Cohort 1 and 2

MAU868 serum concentrations through Week 16 will be evaluated by the SSRC for both Cohorts 1 and 2. The pharmacokinetic analyses will be performed by another vendor and described in a standalone PK analysis plan.

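### SAP 7.5.1.7 measures and tests the rate of viral-load decrease in raw copies/mL, so the subjects with the highest baselines dominate it; it should be on the log10 scale with baseline as a covariate

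*SAP*

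**What the plan says.** SAP 7.5.1.7 defines the endpoint as "Rate of decrease = Change from baseline (copies/mL) / time (weeks) between baseline and post-baseline". The treatment difference "will be assessed at the specified visit with LOCF using an ANOVA model with treatment (four levels) as a factor". There is no baseline term and no transformation. In addition, "the pairwise treatment differences will be analysed using the two-sample t test", with the p-value reported. Residual normality is checked, and "If data shows significant deviation from normality, the Wilcoxon rank sum test will be applied if necessary". The imputation rules in SAP 7.1.5 also work in copies/mL, with 25 assigned to a result that is not detected.

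The same quantity appears in two other places. SAP 7.5.2.3 summarises "The BKV plasma and urine viral load, change from baseline and rate of decrease over time" descriptively. SAP 8.2.2 lists "Rate of decrease in BKV plasma viral load by 1 week, 2 weeks, 4 weeks, 8 weeks, and 12 weeks" for the second interim analysis, analysed as in section 7.5.1.

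SAP 7.5 states: "Efficacy analyses will be conducted using two sided tests at the alpha=0.05 level of significance, with no adjustment for multiplicity". The planned numbers in SAP section 3 are "24 MAU868 and 12 placebo; 8 MAU868 and 4 placebo per cohort", so each dose group of 8 is compared with 12 pooled placebo subjects. The same section says that the study is not powered for efficacy.

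**The concern.** Protocol inclusion criterion 3 and the SAP 7.2.2 MITT definition put the lowest baseline at 10^3 copies/mL, and exclusion criterion 2 puts the highest just under 10^7. That is a 10,000-fold range. An absolute change in copies/mL cannot be much larger than the baseline unless load rises, so differences between subjects in this score are mostly differences in baseline. In arms of 8, one or two high-load subjects can set the arm mean.

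This is the only viral-load endpoint tested as a continuous variable. It should therefore make the fullest use of a small sample, and on the raw scale it does not. It is also among the results given to the SSRC at the second interim, after which the Cohort 3 regimen may be adjusted (SAP sections 5 and 8.2).

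**Working it through.** The plan states no power, effect size or SD for this endpoint, so there is no figure to reproduce. The allocation is consistent: 3 × (8 + 4) = 36, 3 × 8 = 24, 3 × 4 = 12.

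**Step 1: what the score measures.** Count falls as positive. For baseline B and a fall of d log10 units, the 12-week score is B × (1 − 10^−d) / 12.

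- d = 1 gives 0.90 B/12 and d = 2 gives 0.99 B/12. A second log of effect adds 10% (0.99/0.90 = 1.10), whereas B may vary 10,000-fold.
- d = 0.5 gives 0.684 B/12 and d = 1.5 gives 0.968 B/12. At equal baseline, a full log of extra effect multiplies the score by only 0.968/0.684 = 1.42.

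**Step 2: two subjects over 12 weeks.**

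- 5,000,000 to 2,500,000: fall of log10(2) = 0.30 log; score 2,500,000/12 = 208,333 copies/mL/week.
- 20,000 to not detected (25): fall of log10(800) = 2.90 log; score 19,975/12 = 1,665.
- Ratio 208,333/1,665 = 125, in favour of the smaller virological response.

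**Step 3: effect on the tests.** Inputs from the documents: groups of 12/8/8/8, two-sided 0.05, baseline limits 10^3 to 10^7, floor of 25 copies/mL, Week 12. Assumptions not in the documents: baseline log10 load normal with mean 4.5 and SD 0.5 or 0.8, truncated to the limits; SD of individual log10 change 0.8 (0.9 for the 2-log fall); all three dose groups equally effective; no missing data. Power is the share of 4,000 simulated trials with a significant result favouring drug, for one dose group against pooled placebo. The Monte Carlo standard error is at most √(0.25/4000) = 0.8 points.

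| Baseline SD | Placebo change | Drug change | Raw ANOVA | Raw Wilcoxon | Log10 ANOVA |
|---|---|---|---|---|---|
| 0.8 | −0.5 | −1.5 | 8% | 18% | 76% |
| 0.8 | −0.5 | −2.0 | 10% | 22% | 95% |
| 0.5 | −0.5 | −1.5 | 14% | 22% | 77% |
| 0.5 | −0.5 | −2.0 | 16% | 27% | 95% |
| 0.8 | 0 | −1.5 | 19% | 56% | 98% |
| 0.8 | +0.3 | −1.5 | 26% | 81% | 99.8% |
| 0.5 | 0 | −1.5 | 32% | 62% | 98% |
| 0.5 | +0.3 | −1.5 | 45% | 85% | 99.9% |

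Shapiro-Wilk rejected normality of the raw residuals in 95–99.5% of trials, so the condition for the fallback would nearly always be met.

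The raw mean difference pointed the wrong way in 8–21% of trials when placebo fell and in 0.3–5% otherwise. On the log10 scale it did so in 0.4% or fewer.

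**Step 4: why the rank test helps only sometimes.** If placebo also falls, both arms' scores are close to their baselines (step 1), and ranking raw values ranks baselines. If placebo is flat or rising, its scores scatter around zero or take the opposite sign, and ranks then separate the arms.

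**The case against.** The strongest reply is that the SAP anticipates non-normality. The Wilcoxon condition would be met in nearly every trial, and with placebo flat or rising the rank test has moderate to good power. That stands, and it rules out a reading that a reader might otherwise take from the ANOVA figures: that this endpoint cannot detect an effective drug. The documents do not give the baseline spread, the SD of change or the placebo course, so that reading is not supported.

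Three limits remain. A falling placebo arm is plausible, because SAP 2.2.1 allows immunosuppression to be reduced up to and including the Baseline Visit, and Protocol 1.1 describes such reduction as the recommended way to control the infection. Use of the fallback is left to judgement after the data are seen. And a rank test does not repair the least squares means, confidence intervals, t tests or raw-scale summaries.

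A second reply is that little depends on this endpoint. The primary objective is safety. This is one of twelve efficacy endpoints in SAP 6.1.2 and one of ten at the second interim. Six of the twelve cover plasma load through a 1-log, <LLOQ or <LOD criterion and do not share the problem. No rule ties the Cohort 3 regimen to this p-value; the SSRC and sponsor also see the other endpoints and individual patient profiles. All of this is correct and limits the severity. It is not a reason to keep the raw scale.

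A reader might also infer that chance imbalance could produce a false finding of harm. Wrong-sign estimates do occur, but significant results in the wrong direction were seen in 0.1% of simulated trials or fewer. The risk is a noisy, hard-to-read estimate.

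Log10 has its own limit: with a floor of 25, a subject starting at 10^3 can fall by at most log10(1000/25) = 1.6 log. The simulation includes that floor, and log10 still did better in every scenario.

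**Conclusion.** The point stands as a fault of scale in one secondary endpoint. That the raw-copies rate is dominated by high baselines follows from the SAP formula and the eligibility range alone. The size of the power loss rests on the assumptions in step 3:

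- Placebo falling 0.5 log, drug falling 1.5 to 2 log: about 8–16% for raw ANOVA, 18–27% for raw Wilcoxon, 76–95% for log10 ANOVA.
- Placebo flat or rising 0.3 log, drug falling 1.5 log: about 19–45%, 56–85% and 98–99.9%.

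These figures are for 8 versus 12. At the second interim the pooled placebo group is only 4 + 4 = 8, which I did not simulate.

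It should be fixed before unblinded use. A reader might conclude that the trial's viral-load evidence as a whole, or the Cohort 3 decision, is compromised. The documents do not support that: the threshold endpoints are sound, and no decision rule depends on this test.

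**What to change.** - **SAP 7.5.1.7, and by reference 8.2.2:** define the rate as change from baseline in log10 copies/mL divided by weeks. Analyse it by ANCOVA with treatment and baseline log10 viral load, and report adjusted mean differences with confidence intervals on that scale.
- **SAP 7.5.2.3:** present viral-load summaries and plots as mean log10 values or geometric means.
- **Rank test:** replace the discretionary switch with a prespecified sensitivity analysis on the log10 change, reported whatever the normality check shows.

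The cost is SAP wording, a few lines of programming and one error degree of freedom (36 − 4 = 32 becomes 31). No new data are needed. Record the change in SAP section 9.
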